9.2 Test and observation timepoints

9.2.1 Subject background

The following subject background factors will be determined and recorded in the CRF.

- (1) Sex
- (2) Date of birth (western calendar)
- (3) Height
- (4) Race
- (5) Ethnicity
- (6) Smoking status
- (7) Underlying cause of CKD
- (8) Time of onset of nephrogenic anaemia
- (9) Concomitant illnesses (illnesses present on the first day of the treatment period)
- (10) Start time of hemodialysis
- (11) Type of hemodialysis*¹ (hemodialysis or hemodiafiltration)
- (12) Frequency of hemodialysis*² (times/week)
- (13) Hemodialysis conditions (dialyzer, dialysate, type of anticoagulant)
- (14) ESA formulation washout (yes/no)
- (15) Type, administration route, dose interval, dosage, and final day of ESA formulation washed out

*1: If the type of hemodialysis is changed at any point from the first day of the treatment period to the final day of the follow-up observation period, the date of the change and the type after the change should be recorded in the CRF.

*2: If the frequency of hemodialysis is changed at any point from the first day of the treatment period to the final day of the follow-up observation period, the date of the change and the frequency after the change should be recorded in the CRF.

9.2.2 Treatment status

The following information should be recorded in CRFs.

- (1) MT-6548 dosage (details and reasons for change if there was a change of dosage or drug holiday)
- (2) First day of MT-6548 treatment and final day of MT-6548 treatment
- (3) MT-6548 treatment compliance status
- (4) Timing of MT-6548 doses (pre-prandial: within 30 minutes prior to eating; post-prandial: within 30 minutes of eating (including eating); other)

(5) MT-6548 dose date and time*

* Date and time of dose immediately prior to blood sampling for EPO measurement at treatment period Weeks 2, 4, 12, and 24, and day of discontinuation.

9.2.3 Efficacy endpoints

Blood sampling will be performed at each study center for measurement by the contract laboratory testing facility. Study centers will store test reports issued by the contract testing laboratory.

During the screening period, blood will be collected before dialysis whenever the subject makes a study visit on the same day they are scheduled for dialysis. During the treatment period, blood will be collected before dialysis on days the subject is scheduled for dialysis.

(1) Hb value

Blood sampling and Hb measurement will be performed in the supine position on the first day of the screening period, screening period Visit 2, the first day of the treatment period, Weeks 2, 4, 6, 8, 10, 12, 16, 20, and 24 of the treatment period, and the day of discontinuation of treatment.

(2) Ratio of subjects who received ESA rescue therapy

If ESA rescue therapy is performed, type of ESA formulation used, administration route, dose interval, and dosage will be recorded in the CRF.

(3) Ratio of subjects who received red blood cell (RBC) transfusion rescue therapy.

If RBC transfusion rescue therapy is performed, type of RBC formulation used and dosage will be recorded in the CRF.

(4) Study drug dosage

Study drug dosage will be recorded in CRFs.

(5) Total number of dosage adjustments

Yes/no for study drug dosage adjustments and post-adjustment dosage will be recorded in the CRF.

(6) Quantity of iron administered

Iron dosage will be recorded in CRFs.

(7) Iron-related measures (serum iron, TIBC, TSAT, and serum ferritin)

Blood sampling and measurement will be performed for serum iron, TIBC, TSAT, and serum ferritin on the first day of the screening period, the first day of the treatment period, Weeks 2, 4, 6, 8, 10, 12, 16, 20, and 24 of the treatment period, and the day of discontinuation of treatment.

(8) Hepcidin

Blood sampling and measurement of hepcidin will be performed on the first day of the treatment period, treatment period Weeks 2, 4, 6, 12, and 24, and the day of discontinuation of treatment.

(9) Haematocrit, RBC count

Blood sampling and measurement will be performed for haematocrit and RBC count on the first day of the screening period, the first day of the treatment period, Weeks 2, 4, 6, 8, 10, 12, 16, 20, and 24 of the treatment period, and the day of discontinuation of treatment.

(10) Reticulocytes (counts and fractions)

Blood sampling and measurement will be performed for reticulocytes (counts and fractions) on the first day of the screening period, the first day of the treatment period, Weeks 2, 4, 6, 8, 10, 12, 16, 20, and 24 of the treatment period, and the day of discontinuation of treatment.

(11) EPO

Blood sampling and measurement of EPO will be performed on the first day of the treatment period, treatment period Weeks 2, 4, 6, 12, and 24, and the day of discontinuation of treatment. Blood sampling time will be recorded in CRFs.

(12) QOL measures (EQ-5D-5L, KDQOL)

Subjects will fill out EQ-5D-5L and KDQOL questionnaires (Appendices 4 and 5) on the first day of the treatment period, treatment period Weeks 12 and 24, and the day of discontinuation of treatment, and results recorded in CRFs.

9.2.4 Safety endpoints

9.2.4.1 Objective findings

(1) Laboratory tests

The following laboratory parameters will be measured at a contract testing laboratory following blood collection at the study center. Study centers will store test reports issued by the contract testing laboratory.

During the screening period, blood will be collected before dialysis whenever the subject makes a study visit on the same day they are scheduled for dialysis. During the treatment

period, blood will be collected before dialysis on days the subject is scheduled for dialysis. Only urea nitrogen levels should be measured before and after dialysis on the first day, Week 24 of the treatment period, and on the day of treatment discontinuation.

Investigators/subinvestigators will record day of confirmation and confirmation results (clinical significance) for the following tests.

1) Haematology tests:

Blood sampling and measurement will be performed for the following parameters on the first day of the screening period, the first day of the treatment period, Weeks 2, 4, 6, 8, 10, 12, 16, 20, and 24 of the treatment period, and the day of discontinuation of treatment.

Parameters: Mean corpuscular volume, mean cell haemoglobin, mean cell haemoglobin concentration, red cell distribution width, WBC count, WBC fraction (neutrophils, eosinophils, monocytes, lymphocytes, basophils), platelet count

2) Blood biochemistry tests:

Blood sampling and measurement will be performed for the following parameters on the first day of the screening period, the first day of the treatment period, Weeks 2, 4, 6, 8, 10, 12, 16, 20, and 24 of the treatment period, and the day of discontinuation of treatment. Only urea nitrogen levels should be measured before and after dialysis on the first day, Week 24 of the treatment period, and on the day of treatment discontinuation.

Parameters: Total protein, albumin, blood glucose, urea nitrogen, creatinine, uric acid, CPK, total bilirubin, AST, ALT, ALP, LDH, γ -GTP, Na, K, Cl, Ca, P, Mg, bicarbonate, total cholesterol, LDL-C, HDL-C, triglycerides

3) C-reactive protein:

Blood sampling and measurement of C-reactive protein will be performed on the first day of the screening period, the first day of the treatment period, treatment period Week 24, and the day of discontinuation of treatment.

4) Folic acid and vitamin B₁₂:

Blood sampling and measurement of folic acid and vitamin B₁₂ will be performed on the first day of the screening period.

5) Vascular endothelial growth factor (VEGF)

Blood sampling and measurement of VEGF will be performed on the first day of the screening period, treatment period Weeks 12 and 24, and the day of discontinuation of treatment.

(2) Resting standard 12-lead ECG

Resting standard 12-lead ECG will be measured in the supine position during hospital visits on the first day of the treatment period, treatment period Week 24, and the day of discontinuation of treatment. ECG diagnosis consists of a comprehensive evaluation including arrhythmia and wave-form diagnoses.

Measured to extent possible prior to blood sampling before dialysis on the day of dialysis. Measurements will be made before blood sampling when possible, and after 5 minutes at rest.

- 1) Normal
- 2) Clinically non-problematic abnormality
- 3) Clinically problematic abnormality

(3) Dry weight

Dry weight will be measured during study visits on the first day of the treatment period, treatment period Weeks 12 and 24, and the day of discontinuation of treatment. Measurements are recorded in CRFs.

(4) Body weight

Body weight will be measured before and after dialysis during study visits on the first day of the treatment period, treatment period Weeks 12 and 24, and the day of discontinuation of treatment. Measurements are recorded in CRFs.

(5) Duration of hemodialysis

The duration of hemodialysis during visits on the first day, Week 24 of the treatment period, and on the day of treatment discontinuation should be recorded in CRFs.

(6) Vital signs

Sitting blood pressure and pulse rate will be measured during study visits on the first day of the treatment period, treatment period Weeks 2, 4, 6, 8, 10, 12, 16, 20, and 24, and the day of discontinuation of treatment.

During the screening period, measurements will be made before dialysis whenever the subject makes a study visit on the same day they are scheduled for dialysis. During the treatment period, measurements will be made before dialysis on days the subject is scheduled for dialysis. Measurements will be made before blood sampling when possible, and after 5 minutes at rest.

(7) Fundoscopy

Fundoscopy will be performed once each within the screening period, from treatment period Week 20 to Week 24, and to extent possible within 14 days of study withdrawal. An ophthalmologist will perform the fundoscopy and make evaluations according to the 3-point scale below. Ophthalmologist evaluations will be recorded in CRFs. Fundoscopy images and ophthalmologist evaluations will be stored at study centers.

- 1) Normal
- 2) Clinically non-problematic abnormality
- 3) Clinically problematic abnormality (retinal hemorrhage yes/no, retinal oedema yes/no)

(8) Chest X-ray

Fundoscopy will be performed once each within the screening period, from treatment period Week 20 to Week 24, and to extent possible within 14 days of study withdrawal. Investigators/subinvestigators will evaluate test results according to the 3point scale below. Evaluation results will be recorded in CRFs. Chest X-rays will be stored at the study center.

- 1) Normal
- 2) Clinically non-problematic abnormality
- 3) Clinically problematic abnormality

(9) Pregnancy tests (only for women who may become pregnant)

Blood sampling and pregnancy testing will be performed on the first day of the screening period, treatment period Week 24, and the day of discontinuation of treatment. Investigators/subinvestigators will evaluate pregnancy based on test results and interview when appropriate. Evaluation results will be recorded in CRFs. If the subject is incapable of becoming pregnant, the reason for this will be recorded in CRFs (women only).

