5.3.2 Safety endpoints

- (1) Adverse events and adverse drug reactions
- (2) Laboratory test values
- (3) Resting standard 12-lead ECG
- (4) Dry weight
- (5) Body weight
- (6) Vital signs
- (7) Fundoscopy
- (8) Chest X-ray
- (9) Proportion of subjects with documented Hb levels of ≥ 12.0 or ≥ 13.0 g/dL
- (10) Ratio of subjects with Hb increase rates exceeding 0.5 g/dL/week.

Rationale

- (1)–(6) (8) Set to evaluate general safety for HD-CKD patients.
- (7) Set to evaluate effects of MT-6548 on fundus oculi.
- (9) (10) Set to evaluate excessive or acute increase of Hb levels.

6. Target sample size and study period

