13.3.3 Safety

(1) Analysis methods for AEs and ADRs

The following statistics will be shown: numbers of subjects and incidence ratios for AEs, SAEs, AEs leading to discontinuation, AEs leading to death, ADRs, serious ADRs, ADRs leading to discontinuation, and ADRs leading to death.

(2) Analysis methods for laboratory values, resting standard 12-lead ECG, dry weight, body weight, vital signs, fundoscopy, and chest X-ray

Descriptive statistics will be calculated for continuous data at each timepoint. Descriptive statistics will also be calculated for changes from baseline. A shift table will be shown for changes of discrete data from baseline to each timepoint.

(3) Analysis methods for ratios of subjects with Hb levels of ≥ 12.0 g/dL or ≥ 13.0 g/dL.

Numbers and ratios of subjects with Hb levels of ≥ 12.0 g/dL or ≥ 13.0 g/dL at each timepoint will be shown.

- (4) Ratio of subjects with Hb increase rates exceeding 0.5 g/dL/week.

Numbers and ratios of subjects with rate of Hb increase of >0.5 g/dL/week will be shown.

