Table 14.3.1.10 Adverse Events by Severity by System Organ Class and Preferred Term (Safety Analysis Set)
Table 14.3.1.11 Adverse Drug Reactions by Severity by System Organ Class and Preferred Term (Safety Analysis Set)
Table 14.3.1.12 Adverse Events by Timing of Onset by System Organ Class and Preferred Term (Safety Analysis Set)
Table 14.3.1.13 Adverse Drug Reactions by Timing of Onset by System Organ Class and Preferred Term (Safety Analysis Set)
Table 14.3.1.14 Adverse Events by Dose of Study Drug at Onset by System Organ Class and Preferred Term (Safety Analysis Set)
Table 14.3.1.15 Adverse Drug Reactions by Dose of Study Drug at Onset by System Organ Class and Preferred Term (Safety Analysis Set)
Table 14.3.1.16 Adverse Events by Cumulative Dose of Study Drug at Onset by System Organ Class and Preferred Term (Safety Analysis Set)
Table 14.3.1.17 Adverse Drug Reactions by Cumulative Dose of Study Drug at Onset by System Organ Class and Preferred Term (Safety Analysis Set)
Table 14.3.1.18 Adverse Events Occurred during 4 Weeks before or 4 Weeks after

Interruption of Study Drug by System Organ Class and Preferred Term (Safety Analysis Set)
Table 14.3.1.19 Adverse Drug Reactions Occurred during 4 Weeks before or 4 Weeks after Interruption of Study Drug by System Organ Class and Preferred Term (Safety Analysis Set)
Table 14.3.2.1 Laboratory Test: Absolute and Change from Baseline (Safety Analysis Set)
Table 14.3.3.1 12-lead Electrocardiogram: Clinical Findings (Safety Analysis Set)
Table 14.3.3.2 12-lead Electrocardiogram: Shift Table of Clinical Findings (Safety Analysis Set)
Table 14.3.4.1 Weight after Hemodialysis: Absolute and Change from Baseline (Safety Analysis Set)
Table 14.3.4.2 Dry weight: Absolute and Change from Baseline (Safety Analysis Set)
Table 14.3.4.3 Kt/V: Absolute and Change from Baseline (Safety Analysis Set)
Table 14.3.5.1 Vital Sign: Absolute and Change from Baseline (Safety Analysis Set)
Table 14.3.6.1 Ophthalmic Test: Clinical Findings (Safety Analysis Set)
Table 14.3.6.2 Ophthalmic Test: Shift Table of Clinical Findings (Safety Analysis Set)
Table 14.3.7.1 Chest X-ray Test: Clinical Findings (Safety Analysis Set)
Table 14.3.7.2 Chest X-ray Test: Shift Table of Clinical Findings (Safety Analysis Set)
Table 14.3.8.1 Hb: Proportion of Subjects with Hb $\geq 12.0$ g/dL or Hb $\geq 13.0$ g/dL (Safety Analysis Set)
Table 14.3.8.2 Hb: Proportion of Subjects with Hb $< 9.0$ g/dL or Hb $< 8.0$ g/dL (Safety Analysis Set)

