#### **7.6.6 Fundoscopy**

The frequency of each decision result (normal, clinically nonsignificant abnormal, or clinically significant abnormal [presence or absence of retinal hemorrhage, presence or absence of retinal edema]) should be calculated at each evaluation time point, and a shift table composed of the decision

results (normal, clinically nonsignificant abnormal, or clinically significant abnormal) should be provided on the first day of the treatment period and each evaluation time point.

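### Retinal haemorrhage and oedema are recorded only under a "clinically problematic" fundus rating, so the lesion-specific count depends on that rating and can only under-count

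*Protocol*

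**What the plan says.** Protocol 5.3.2 lists fundoscopy as a safety endpoint with its own rationale: "Set to evaluate effects of MT-6548 on fundus oculi". The other examinations in that list, such as ECG and chest X-ray, are there for general safety.

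Under Protocol 9.2.4.1 (7), fundoscopy is done once in screening, once between Weeks 20 and 24, and where possible within 14 days of withdrawal. An ophthalmologist assigns one of three ratings: normal; "Clinically non-problematic abnormality"; or "Clinically problematic abnormality (retinal hemorrhage yes/no, retinal oedema yes/no". Only the third carries the lesion items. The rating goes to the CRF, and "Fundoscopy images and ophthalmologist evaluations will be stored at study centers". No central reading is described.

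For the analysis, Protocol 13.3.3 states: "A shift table will be shown for changes of discrete data from baseline to each timepoint". SAP 7.6.6 asks for "The frequency of each decision result (normal, clinically nonsignificant abnormal, or clinically significant abnormal", with the lesion items again inside the last category: "clinically significant abnormal [presence or absence of retinal hemorrhage, presence or absence of retinal edema". Its shift table uses the three ratings without the lesion items. The output list in the SAP errata has one findings table and one shift table for this test, the latter being "Table 14.3.6.2 Ophthalmic Test: Shift Table of Clinical Findings (Safety Analysis Set".

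**The concern.** Haemorrhage and oedema are the only retinal lesions the plan names, so the sponsor evidently wants them counted. As written, the count is of lesions that were both present and judged clinically problematic. That judgement is made locally, in an open-label, uncontrolled study. Two lesions of the same kind can be recorded differently depending on the examiner's view of their importance.

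There is one examination before treatment and one on treatment, and 20 subjects are planned, so each subject missed is 5 percentage points (1/20). A low or zero haemorrhage row could be read as a statement about haemorrhage when it is a statement about problem-rated haemorrhage. The conditioning works in one direction: it can remove a lesion from the count but cannot add one.

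**Working it through.** The plan gives no rate, precision or power for the fundus endpoint, and Protocol 6.1 justifies the sample size by feasibility. There is no planned figure to reproduce. The check has two parts.

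**1. Where a new haemorrhage or oedema at Week 20–24 would appear**

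Ratings are 1 = normal, 2 = non-problematic abnormality, 3 = problematic abnormality.

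| Screening → on treatment | Shift table (SAP 7.6.6) | Lesion yes/no count |
|---|---|---|
| 1 → 2 | Change shown, lesion type lost | Not counted |
| 2 → 2 | No change | Not counted |
| 1 or 2 → 3 | Change shown | Counted |
| 3 → 3 | No change | Counted at that time point, but not identified as new |

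The 2 → 2 row can occur. Exclusion criterion (9) bars active fundus disease and eyes in which no findings can be obtained; it does not bar an inactive abnormality. Diabetes and hypertension are among the CKD causes and complications listed in SAP Table 7.3, so a screening rating of 2 is plausible. The documents do not say how common it will be.

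**2. How much the conditioning could matter (illustration only)**

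Inputs:
- n = 20 (Protocol 6.1), taking every subject to have an on-treatment examination.
- p = true incidence of a new lesion. Not in the documents; assumed 5%, 10% or 20%.
- s = share of those lesions rated 3. Not in the documents; assumed 100%, 75%, 50% or 25%.

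The recorded rate is p × s, so P(recorded 0/20) = (1 − p × s)^20.

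With p = 10%:
- s = 100%: 0.900^20 = 12.2%
- s = 75%: 0.925^20 = 21.0%
- s = 50%: 0.950^20 = 35.9%
- s = 25%: 0.975^20 = 60.3%

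The first line is the chance of no true case. Subtracting it gives the chance of at least one true case with none recorded: 8.9%, 23.7% and 48.1% for s = 75%, 50% and 25% (differences taken before rounding).

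Varying the incidence at s = 50%:
- p = 5%: 0.975^20 = 60.3%
- p = 20%: 0.900^20 = 12.2%

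A recorded 0/20 has an exact two-sided 95% upper limit of 1 − 0.025^(1/20) = 16.8%. That limit applies to p × s, the rate of problem-rated lesions, and not to p.

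**The case against.** A reader might infer that a lesion rated 2 is never counted, or that the fundus endpoint can read zero by construction. The documents support neither.

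- The endpoint is the whole three-level evaluation. SAP 7.6.6 tabulates all three ratings and their shifts, so a normal eye that develops a lesion rated 2 is shown as having changed. Only the type of lesion is lost.
- Even the lesion count is forced to zero only if every lesion is rated non-problematic.
- In a subject rated 3 at both examinations the items are asked both times, so a new haemorrhage still raises the count at Week 20–24.

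There is also a separate route. Under Protocol 9.2.4.2 the investigator decides whether an objective finding is an adverse event, and nothing there makes the ophthalmologist's rating binding. Events are named by diagnosis where possible and tabulated by SOC and PT (SAP 7.6.1.2), so a reported retinal haemorrhage would appear by name. This stands in part. A lesion with symptoms, treatment or a change in study drug meets the criteria in that section. A symptomless, untreated lesion that changes nothing about dosing is left to the investigator's own view of whether it is clinically problematic, which is close to the same filter.

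It is also fair to say that a specialist's significance rating is a legitimate choice, used for ECG and chest X-ray as well, and that 20 uncontrolled subjects cannot establish attribution to the drug. That limits what the extra data can prove. It is not a reason to condition the count of the two named signs on a judgement. Finally, neither the CRF page nor the SAP's list of subject listings is in the available text, so the form may already ask more than the protocol states.

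**Conclusion.** The point holds as a weakness in how the lesions are recorded and counted. Both documents attach the haemorrhage and oedema items to rating 3 alone. The resulting count can therefore only understate the number of subjects with the sign, and it does not separate new from old lesions. The gap is widest for a subject rated 2 at both examinations, where a new lesion leaves no trace in either planned fundus table.

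The size cannot be fixed from the documents. The probabilities above are correct arithmetic on an assumed incidence and assumed rating shares, and they show that a zero row would be weak evidence if a sizeable share of lesions is rated non-problematic. The endpoint as a whole remains informative. This is a cheap improvement to the one test included specifically to look for effects on the fundus, and it does not invalidate the safety analysis.

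**What to change.** - **Protocol 9.2.4.1 (7) and the CRF:** have the ophthalmologist answer retinal haemorrhage yes/no and retinal oedema yes/no at every planned examination, whatever the three-level rating.
- **SAP 7.6.6:** beside the existing shift table, report for each sign the number and proportion of subjects in whom it was absent at screening and present at Week 20–24 or discontinuation, with an exact (Clopper–Pearson) 95% CI. Use the screening examination as baseline, since it is the only one planned before treatment.
- **Examinations already done:** fill in the two items only where the stored ophthalmologist evaluation already states them. Do not re-read images, which could need an additional reader. Report how many examinations lack the items.

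The cost is two tick boxes on about 40 examinations (20 subjects × 2) and two table rows, with no extra procedure. The small downside is that some minor or old lesions will be listed; the absent-at-screening condition keeps lesions already recorded at screening out of the new-onset count. If the CRF already asks both items at every rating, only the SAP needs to change.
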